## **13.2. Reporting of Serious and Non-Serious Adverse Events**

### 13.2.1. General Reporting Requirements (Serious & Non-Serious Adverse Events)

All serious and potentially device- and/or procedure-related adverse events must be recorded on the Adverse Event eCRF by the Investigator (or designee). The report should include: severity, duration, action taken, treatment outcome and relationship of the adverse experience to the study device, procedure, concomitant medications, pre-existing condition, etc. (i.e., unrelated, related or relationship unknown).

In the case of serious adverse events, procedure and/or device observations and malfunctions, medical record documentation (e.g. procedure notes, operative notes, discharge summary, relevant progress notes, imaging or lab studies) must be provided to Cardiva Medical or its designee.

*The following criteria must also be adhered to by the Investigator in the case of serious adverse events:*

- It is the responsibility of the Investigator to inform their IRB of serious adverse events as required by their IRB's procedures and in conformance with FDA and local regulatory requirements.

All serious device- and/or procedure-related adverse events must be reported by the Investigator (or designee) to the Sponsor within 24 hours of learning of the adverse event via eCRF. The Cardiva Medical contact information for questions is:

Sponsor: Cardiva Medical, Inc.  
[name]  
[name]  

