#### Secondary Safety Analysis

The combined incidence rate and individual complication incidence rates will also be reported by treatment received for access site closure related minor complications. Formal non-inferiority testing will not be conducted for minor complications.

Additionally, all reported adverse events will be summarized by treatment regardless of relationship to access site closure.

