## **13. Adverse Events**

### **13.1. General**

All adverse events (AE) and serious adverse events (SAE) will be monitored from the time of randomization through the 1-month follow-up visit.

An AE is defined as any undesirable clinical occurrence in a patient whether or not it is considered to be device related. In addition, the definition of AE applies to any event with an onset post study procedure or to any underlying diseases present at baseline, that exacerbate in severity post study procedure. Therefore, an underlying disease that was present at the time of enrollment is not reported as an AE, but any increase in the severity of the underlying disease is to be reported as an AE. This definition includes events occurring during the follow-up period.

All reported AEs must be recorded in the electronic database. A description of the event, including the start date, resolution date, action taken, and the outcome should be provided, along with the Investigator's assessment of the relationship between the AE, the study treatment and the study procedure.

The following definitions for rating severity of adverse events will be used:

Mild:	Awareness of signs or symptoms, but easily tolerated; are of minor irritant type; causing no loss of time from normal activities; symptoms would not require medication or a medical evaluation; signs or symptoms are transient.
Moderate:	Interferes with the subject's usual activity and/or requires symptomatic treatment.
Severe:	Symptom(s) causing severe discomfort and significant impact of the subject's usual activity and requires treatment.

A serious adverse event (SAE) is defined as an event which leads to:

- Death due to any cause
- Life-threatening condition
- Results in persistent or significant disability/incapacity
- Requires in-patient hospitalization or prolonged hospitalization
- Results in congenital abnormality

All SAE's will be reported.

**Device-Related Adverse Event:** an adverse event is considered to be device-related when, in the judgment of the Investigator, the clinical event has a reasonable time sequence associated with use of the investigational device and is unlikely to be attributed to concurrent disease or other procedures or medications. It is reasonable to believe that the device directly caused or contributed to the adverse event.

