### **16.2. Source Documentation**

The Principal Investigator must maintain detailed source documents on all trial subjects who are enrolled in the trial or who undergo screening. Source documents include subject medical records, hospital charts, clinic charts, Investigator's subject trial files, as well as the results of diagnostic tests (e.g., laboratory tests).

The following minimum information should be recorded in the subject's source records:

- The date the subject entered the study and the subject ID number
- The study name
- The date that informed consent was obtained
- Evidence that the subject meets trial eligibility requirements (e.g., medical history, trial procedures and/or evaluations)
- The dates of all trial related subject visits
- Evidence that required procedures and/or evaluations were completed
- Documentation of specific investigational devices used, if any
- Occurrence and status of any Adverse Events
- The date the subject exited the study, and a notation as to whether the subject completed the study or was discontinued, including the reason for discontinuation.

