#### **SERIOUS ADVERSE EVENTS (SAEs)**

The Investigators will report by eCRF any SAEs including serious, and/or potentially device- or procedure-related adverse events as soon as possible, within 24 hours of the Investigator becoming aware of the event, to the Sponsor and the Sponsor's CRO and to the IRB as per the committee's reporting requirements. The Serious Adverse Event eCRF is to be completed and submitted to the Sponsor as initial notification.

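### Section 13.2.1 makes the AE eCRF mandatory only for serious or possibly related events, so the by-treatment AE summary in 9.2.3 may be selectively filled for non-serious events

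*Combined protocol and SAP*

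**What the plan says.** Section 13.1 is broad. It defines the term as follows: "An AE is defined as any undesirable clinical occurrence in a patient whether or not it is considered to be device related". It sets the observation period: "All adverse events (AE) and serious adverse events (SAE) will be monitored from the time of randomization through the 1-month follow-up visit". It then gives the recording rule: "All reported AEs must be recorded in the electronic database". Section 16.2 likewise asks that the source record hold "Occurrence and status of any Adverse Events".

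Section 13.2.1, whose heading covers both serious and non-serious events, states the duty to complete the form more narrowly: "All serious and potentially device- and/or procedure-related adverse events must be recorded on the Adverse Event eCRF by the Investigator (or designee". The 24-hour reporting paragraph in Attachment 1 (section 20.3) uses a similar set: "any SAEs including serious, and/or potentially device- or procedure-related adverse events".

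The analysis that draws on these data is in section 9.2.3, Secondary Safety Analysis: "all reported adverse events will be summarized by treatment regardless of relationship to access site closure".

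**The concern.** The analysis text promises a table that does not depend on relationship, while one of the two capture rules makes entry of non-serious events depend on it. Section 13.1 leaves device and procedure relationship to the investigator's judgment. The investigator carries out or supervises the assigned closure and so cannot be blind to arm. If the threshold for calling a non-serious event possibly related differs between the arms, the arms will enter different fractions of the same underlying events, and the reader of the table will have no means of seeing it.

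The AE summary is where the report shows events outside the closure-related endpoint lists. A relationship-free summary is useful because it does not rest on anyone's attribution, and that property is lost for the non-serious part if the form was completed under 13.2.1.

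**Working it through.** The point depends on no sample size, margin or event rate, so the check is a comparison of text.

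**Step 1: which events each rule covers.**

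| Type of event | 13.1 | 13.2.1 | Other rule |
|---|---|---|---|
| Serious, any relationship | recorded | mandatory | 20.3 also covers it |
| Non-serious, possibly related to device or procedure | recorded | mandatory | reviewed under 14.1 |
| Venous re-bleeding at an access site before discharge | recorded | mandatory if serious or possibly related | 7.4.6 requires an AE record in both arms, with no relationship condition |
| Other non-serious event, judged unrelated to device and procedure | recorded if reported | not mandatory | 16.2 places it in the source record only |

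The rules part company only in the last row.

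**Step 2: can the wording be reconciled?** Section 13.1 speaks of reported events. If that means the events 13.2.1 obliges a site to report, the two sections agree, but the 9.2.3 summary is then drawn from a set already selected on relationship for non-serious events. If it means every event the site learns of, the sections conflict. Either the capture rule or the description of the table needs changing.

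The opening words of 13.2.1 could also be read as requiring an event to be both serious and related, which would be narrower still. The section heading and the wording in 20.3 favour the either/or reading used here.

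**Step 3: what can fall into the last row.** Section 13.1 gives separate categories for events attributed to concomitant medication, with bleeding on anticoagulation as its example, and for events attributed to a pre-existing condition. A non-serious bleed, other than an in-hospital access-site re-bleed, that the investigator puts wholly down to anticoagulation is outside the 13.2.1 duty. For a closure device, that attribution is one that knowledge of the arm could plausibly sway.

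**Step 4: is there a later safeguard?** Apart from the reported endpoint complications, the independent review in 14.1 starts from events that the investigator has already reported as possibly related to device or procedure. It cannot recover an event that was never entered.

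**Step 5: size.** The documents give no expected frequency of non-serious events and no proportion judged unrelated, so neither the size nor the direction of any distortion can be derived.

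**The case against.** The strongest reply is that 13.2.1 sets a floor. It does not contain the word only, it does not cancel 13.1, and a site that follows 13.1 satisfies both. Its heading includes non-serious events and its relationship field allows an answer of unrelated. Source records must hold every adverse event, and monitors check eCRFs against source under 11.1. The summary in 9.2.3 is descriptive, with no test or margin.

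Most of this stands and limits the point: the filter arises only at sites that work to the minimum, and no hypothesis or success criterion is touched. It does not remove the point. A monitor who finds a non-serious, unrelated event in source but not in the database is not told which section governs, so practice may differ between sites.

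Some stronger inferences are tempting but unsupported:

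- **That in-hospital re-bleeding could be lost.** Section 7.4.6 requires an adverse event record for it in both arms, whatever its cause.
- **That vessel perforation or retroperitoneal bleeding could be lost.** After femoral venous access these would ordinarily be serious or at least possibly related, so 13.2.1 already requires entry.
- **That events during device deployment fall outside the definition**, because 13.1 says "the definition of AE applies to any event with an onset post study procedure". That clause is introduced as an addition to the general definition, not a limit on it. Monitoring starts at randomization, and Table 3 in section 7.3 collects adverse events at the index procedure.
- **That a bias can be quantified by assuming different attribution rates for events of uncertain cause.** Those events are possibly related, and 13.2.1 already captures them.

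**Conclusion.** The point holds in a limited form. Sections 13.1 and 13.2.1 set different capture rules. Where sites follow the narrower one, the by-treatment AE summary may be biased for non-serious events that the investigator attributes to something other than device or procedure. The direction is unknown and the amount cannot be estimated from the documents.

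This rests on two assumptions: that at least some sites treat 13.2.1 as the operative rule, and that investigators know the arm, which is inferred from the design and not stated.

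A reader might go further and conclude that the AE table cannot be compared between arms, or that the safety conclusions are at risk. The documents do not support that. Serious events are recorded whatever their relationship. The primary and secondary safety endpoints are closure-related by definition and adjudicated by the DSMC, and an event that might qualify is one that 13.2.1 already requires to be entered.

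**What to change.** Amend the first sentence of 13.2.1 so that all adverse events from randomization through the 30-day visit go on the AE eCRF, whatever their seriousness or relationship. Keep the Non-Events list in 13.1 as the only exception, and keep the relatedness condition for expedited reporting alone. That brings 13.2.1 into line with 13.1 and 16.2 and makes the description in 9.2.3 accurate.

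If the sponsor prefers the narrower capture, reword 13.1 to match and relabel the 9.2.3 summary as limited to serious events and those considered possibly related to device or procedure, so that nobody reads it as free of attribution.

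The first option costs one sentence in the protocol and modestly more AE entry over a 30-day follow-up. The second costs no data entry but gives up the relationship-free summary.

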**[contact]**  
**[contact]**

### **13.3. Device Failures and Malfunctions**

All reported device observations, malfunctions or failures of the Cardiva Mid-Bore VVSC are required to be documented in the eCRF. In the event of a suspected observation or device problem, the investigational device shall be returned to the Sponsor for analysis. Device failures and malfunctions should also be documented in the patient's medical record. Instructions for returning the investigational device are included in the Manual of Operations.

NOTE: Device failures or malfunctions are NOT to be reported as adverse events. However, if there is an adverse event that results from a device failure or malfunction, that specific event would be recorded in the usual way.

## **14. Study Committee**

### **14.1. Data Safety Monitoring Committee (DSMC)**

An independent combination Clinical Events Committee (CEC) and Data Safety Monitoring Board (DSMB), referred to as the Data Safety Monitoring Committee, or DSMC, shall be responsible for systematic review and adjudication of all reported major and minor access site-closure related endpoint complications. All other events reported to be potentially device- or procedure-related by the Investigator will be reviewed by an independent Safety Manager and/or a member of the DSMC to determine whether it meets criteria for adjudication. In order to enhance objectivity and reduce the potential for bias, the DSMC members shall be independent of the Sponsor as well as the investigational sites/ Investigators.

Members shall consist of at least two (2) independent physicians with experience in catheter-based procedures, and a statistician. A third independent physician may be utilized in cases when disparity occurs between the two primary DSMC reviewers.

The methodology for performing these responsibilities shall be developed and outlined in the Adjudication Charter. Operational provisions shall be established to minimize potential bias.

The DSMC may recommend study termination if safety concerns warrant such action. The DSMC will establish guideline criteria for recommending study termination, to the extent that it is possible for the DSMC to predict adverse events or outcomes, before the proposed study begins.

The Safety Manager will maintain contact with the DSMC members to schedule event reviews in order to assure close and timely monitoring of adverse events and outcomes.

## **15. Ethical Considerations**

### ***15.1. Trial Conduct & the Declaration of Helsinki***

The trial will be performed in accordance with the relevant parts of Title 21 CFR Parts 812, 50, 54, 56; the ICH Guidelines for Good Clinical Practices (E6), and any regional and/or national regulations.

### ***15.2. Institutional Review Board/Ethics Committee***

A copy of the protocol, proposed Informed Consent form, other written patient information and any proposed advertising material must be submitted to the IRB for written approval. A copy of the written IRB approval of the protocol and Informed Consent form must be received by Cardiva Medical, Inc. prior to recruitment of patients into the study and shipment of investigational product.

The Investigator must submit and, where necessary, obtain approval from the IRB as well as the FDA and Sponsor, for all subsequent significant protocol amendments and significant changes to the Informed Consent form. The Investigator should notify the IRB of deviations from the protocol or SAEs and UADEs occurring at the site and other SAE/UADE reports received from Cardiva Medical, Inc. in accordance with local procedures.

The Investigator will be responsible for obtaining annual IRB approval and renewal throughout the duration of the study. Copies of the Investigator's reports and the IRB continuance of approval must be sent to Cardiva Medical, Inc.

### ***15.3. Informed Consent Form***

Sample Informed Consent forms are provided in for Roll-In and Randomized subjects in Attachment 2 for the Investigator to prepare for use at his/her site. The Sponsor will review each site's redlines to the ICF and provide written approval prior to site submission of the documents to their respective IRBs. The reviewing IRB must then approve the ICF prior to use. If translations are required for specific populations, the Sponsor will provide certified translations for the site after IRB approval of the site template.

The reviewing IRB, the FDA and the Sponsor must first approve the Informed Consent forms that are used. The Informed Consent forms must be in accordance with the current guidelines as outlined by the Good Clinical Practices (GCP) guidelines and 21 CFR Part 50.

Prior to participation in the clinical trial, each patient must give written Informed Consent after the context of the study has been fully explained to the patient in language that is easily understood by the patient. The patients must also be given the opportunity to ask questions and have those questions answered to their satisfaction.

Written Informed Consent must be recorded appropriately by means of the patient's dated signature on the ICF. The person administering the Informed Consent shall also sign and date the ICF. The patient shall receive a copy of the ICF, and the informed consent process shall be documented in each subject's source record.

#### **15.4. Amending the Protocol**

An Investigator may not make protocol changes without prior approval by Cardiva Medical. All significant protocol changes that may affect the following must be submitted and approved by the FDA before initiating the change:

- validity of the data or information resulting from the completion of the approved protocol;
- relationship of the likely subject risk to benefit relied upon to approve the protocol;
- scientific soundness of the investigational plan, or;
- rights, safety, or welfare of the human subjects involved in the investigation.

The change must be approved by the FDA and submitted and subsequently approved by the site IRB. Cardiva Medical will submit a copy of the protocol amendment to all Investigators for their IRB's to review and ensure the study continues to be conducted consistently across all sites. The investigative sites must send Cardiva Medical a copy of the IRB approval letter for the protocol amendment.

Cardiva Medical may make certain administrative changes to the protocol without prior approval of the FDA or IRB. Cardiva Medical will notify all investigative sites of such changes to ensure the study continues to be conducted consistently across all sites. The site IRB's will be notified of these changes.

#### **15.5. Emergency Actions**

Cardiva Medical, Inc. accepts the right of the Investigator to deviate from the protocol in an emergency when necessary to safeguard the life or the physical well-being of a study patient. The Investigator must give notice of any emergency deviations and justification for the deviation to Cardiva Medical, Inc. and the IRB as quickly as possible after the episode, in any event no later than 24 hours after the emergency.

#### **15.6. Protocol Deviations**

A protocol deviation is defined as an event where the Clinical Investigator or site personnel did not conduct the study according to the protocol.

Investigators shall be required to obtain prior approval from Cardiva Medical clinical study management before initiating deviations from the protocol, except where necessary to protect the life or physical well-being of a subject in an emergency. Such approval shall be documented in writing and maintained in clinical study management and Investigator files. Prior approval is generally not expected in situations where unforeseen circumstances are beyond the Investigator's control, (e.g. subject was not available for scheduled follow-up office visit, blood

sample lost by laboratory, etc.); however, the event is still considered a deviation and will be reported via the appropriate CRF.

Deviations must be reported to Cardiva Medical regardless of whether medically justifiable, pre-approved by Cardiva Medical or taken to protect the subject in an emergency. Subject specific deviations and non-subject specific deviations, (e.g. unauthorized use of an investigational device outside the study, unauthorized use of an investigational device by a physician who has not signed an Investigator agreement or not been trained in the use of the device, etc.), will be reported on the Protocol Deviation case report form. Investigators will also adhere to procedures for reporting study deviations to their IRB in accordance with their specific IRB reporting policies and procedures.

Regulations require that Investigators maintain accurate, complete and current records, including documents showing the dates of and reasons for each deviation from the protocol. For reporting purposes, Cardiva Medical classifies study deviations as major and minor:

*Major deviation:* Any deviation from subject inclusion and exclusion criteria, subject informed consent procedures or unauthorized device use.

*Minor deviation:* Deviation from a protocol requirement such as incomplete/inadequate subject testing procedures, follow-ups performed outside specified time windows, etc. Minor Deviations that continue to occur at an investigational site may be classified as Major Deviations if corrective action is not taken to secure future compliance to the protocol.

Major and/or recurring protocol deviations reported or identified by the monitor will be discussed with the investigative staff to identify root cause and corrective actions to be implemented to prevent recurrence. Investigators are expected to participate in this important activity in a serious and timely manner.

